Short Form (36) Health Survey (SF-36)		X						X		X		X		X		X	X
Functional Assessment of Chronic Illness Therapy – Fatigue (FACIT-Fatigue)			X						X		X		X		X	X	
Physician and patient global assessment Disease Activity			X	X	X	X	X	X	X		X		X		X	X	
Rheumatoid factor	X																
Anti-cyclic citrullinated peptide (CCP) antibodies	X																
Adverse events (AEs) L																→	
Pharmacokinetic (PK) samples M		X	X	X	X	X	X	X		X		X		X		X	X
Pharmacodynamic (PD) biomarker (total sIL-6R) M		X	X	X	X		X	X		X		X		X		X	X
Joint biomarkers (MMP-3, CXCL13) M	X	X	X	X				X						X			
Immunogenicity samples M	X	X		X		X				X				X		X	X

A. All assessments are to be completed prior to study drug administration, except for subjects who discontinue study drug injections. The order of assessments if more than 1 assessment is planned at the same time should be performed according to the following principles: vital signs should be assessed prior to blood sampling; patient reported outcomes should occur prior to the physician's joint evaluation and study drug should be dosed after all other assessments have been performed.

B. All post baseline visits may occur at the indicated week  $\pm$  3 days throughout the trial.

C. The Early Termination Visit is to be performed 2 weeks after the last study drug dosing for subjects who discontinue from the trial for other reasons than described in the efficacy discontinuation criteria (see section 3.2.3.2), unless they discontinue during a study visit, in which that becomes their Early termination Visit. For subjects who will meet the efficacy discontinuation criteria at Week 12, 16, or 20, the visit at which subjects will meet these discontinuation criteria is defined as the Early Termination Visit.

D. To be performed for each subject, except in case the subject enrolls in the open-label extension study (OLE).

- E. Vital signs (assessment after 5 min in supine position) will include height, weight, blood pressure, pulse, and temperature. A height measurement is only required at the Screening Visit. In case (PK) blood sampling is to be performed at the same visit, the vital signs assessment is to be performed prior to the blood sampling.

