Subjects will have visits at the site q2w up to and including Week 24 (or early termination). A Follow-up Visit will be planned 12 weeks after last study drug administration. Note that for subjects who withdrew for reasons of lost to follow-up, informed consent withdrawal, or death will not have any follow-up assessments.

The ACR20 response was chosen as the primary endpoint since this is a broadly accepted clinical response measure to demonstrate reduction in RA signs and symptoms and sensitive enough to differentiate from placebo effects. For details on primary statistical analysis in this study, please refer to section 3.6.4.1.

Note that higher levels of response, as measured by ACR50 and ACR70 response rates, and measures of remission using the DAS28, CDAI, SDAI, as well as the Boolean remission definition, will be used as supportive evidence of efficacy. In addition, endpoints, including ACR responses and disease activity scores, will be documented over time, including earlier time points, before the therapeutic plateau is expected. This will allow evaluation of potential differences in early clinical efficacy between the doses. Other RA domains, such as improvement in physical function and health-related quality of life, will be evaluated using the HAQ-DI, FACIT-Fatigue scale and the SF-36 questionnaires.

Safety and tolerability assessments will include evaluation of AEs (including serious adverse events, infections, injection site and hypersensitivity reactions), laboratory assessment, urinalysis, vital signs, and physical examination.

Additional planned assessments include the determination of ALX-0061 levels in serum, and PD biomarkers (including sIL-6R) in blood. To assess immunogenicity, the presence of ADA will be measured in serum until the Follow-up Visit, with potentially further characterization by modified ADA assay (mADA) and neutralizing antibody assay (nAb).

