### **Study Treatment Allocation**

At the Screening Visit, informed consent will be obtained from all subjects who are deemed potentially eligible for the study, according to the protocol-specified inclusion and exclusion criteria. At randomization, subjects will be reassessed and, if they meet all specified entry criteria, randomized to receive either ALX-0061 or placebo, as described below (also see section [3.3.8](#) for additional information on randomization).

Eligible subjects will be randomly assigned in a 1:1:1:1:1 ratio to 1 of the treatment groups listed below. As the highest dose of ALX-0061 will be administered via 2 injections q2w, subjects in Groups 1-4 will also be administered 2 injections q2w with 1 or both syringes containing placebo depending on the assigned treatment group to maintain the blind (see section [3.1.2](#)):

Group 1 (N=66)	Placebo Placebo s.c. injections (2 syringes [0.5 and 1.0 mL]) at Week 0 and q2w thereafter up to and including Week 22
Group 2 (N=66)	75 mg q4w ALX-0061 75 mg s.c. injections (1 syringe [0.5 mL]) at Week 0 and q4w thereafter up to and including Week 20. To maintain the blind, subjects in this group will also receive placebo s.c. up to and including Week 22 (1 placebo syringe [1.0 mL] at Week 0 and q4w thereafter in combination with the ALX-0061 injection; 2 placebo syringes [0.5 and 1.0 mL] at Week 2 and q4w thereafter).
Group 3 (N=66)	150 mg q4w ALX-0061 150 mg s.c. injections (1 syringe [1.0 mL]) at Week 0 and q4w thereafter up to and including Week 20. To maintain the blind, subjects in this group will also receive placebo s.c. up to and including Week 22 (1 placebo syringe [0.5 mL] at Week 0 and q4w thereafter in combination with the ALX-0061 injection; 2 placebo syringes [0.5 and 1.0 mL] at Week 2 and q4w thereafter).

Group 4 (N=66)

150 mg q2w

ALX-0061 150 mg s.c. injections (1 syringe [1.0 mL]) at Week 0 and q2w thereafter up to and including Week 22. To maintain the blind, subjects in this group will also receive placebo s.c. q2w up to and including Week 22 (1 placebo syringe [0.5 mL]).

Group 5 (N=66)

225 mg q2w

ALX-0061 225 mg s.c. injections (2 syringes [0.5 and 1.0 mL]) at Week 0 and q2w thereafter up to and including Week 22. These subjects will not receive placebo injections.

*Efficacy Discontinuation Criteria at Week 12, 16, or 20*

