#### 150 mg q4w

**Syringe A** with ALX-0061 at Weeks 0, 4, 8, 12, 16, and 20, and syringe A with placebo at Weeks 2, 6, 10, 14, 18, and 22.

**Syringe B** with placebo at Weeks 0, 2, 4, 6, 8, 10, 12, 14, 16, 18, 20, and 22.

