#### 150 mg q2w

**Syringe A** with ALX-0061 at Weeks 0, 2, 4, 6, 8, 10, 12, 14, 16, 18, 20, and 22.

**Syringe B** with placebo at Weeks 0, 2, 4, 6, 8, 10, 12, 14, 16, 18, 20, and 22.

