### 3.6.4. EVALUATION OF EFFICACY PARAMETERS

The primary endpoint is the reduction of signs and symptoms of RA evaluated by calculating the proportion of subjects achieving an ACR20 response at Week 12.

The following efficacy analyses will be performed in addition to the primary analysis:

- The proportion of subjects achieving an ACR response of 20, 50, and 70 over time will be summarized by treatment group.
- ACR-N index of improvement over time will be summarized by treatment group.
- The DAS28 (using CRP and ESR) score over time will be summarized by treatment group.
- The proportion of subjects with EULAR response over time will be summarized by treatment group.
- The change from baseline (absolute change) in disease activity over time will be summarized by treatment group. The following disease activity scores will be used:
  - DAS28 (CRP and ESR)
  - SDAI
  - CDAI
- The proportion of subjects in remission over time will be summarized by treatment group and compared between the groups. The proportion of subjects who maintained in remission at consecutive time points; i.e., at Weeks 12, 16, 20, 24 will be summarized by treatment group.

The following disease remission definitions will be used:

- DAS28 (ESR) < 2.6
- SDAI  $\leq$  3.3
- CDAI  $\leq$  2.8
- Boolean: TJC  $\leq$  1, SJC  $\leq$  1, CRP  $\leq$  1 mg/dL, VASPA  $\leq$  1 (on a 0-10 scale)
- The change from baseline (absolute change) in HAQ-DI over time will be summarized by treatment group.
- The proportion of HAQ-DI responders (i.e., those who have a clinically meaningful improvement from baseline of  $\geq$  0.25 [absolute change] in HAQ-DI) over time will be summarized by treatment group.
- The proportion of subjects with HAQ-DI  $\leq$  0.5, defining normal physical function, over time will be summarized by treatment group.
- The proportion of subjects with HAQ-DI  $\leq$  0.5 (normal physical function) with or without remission (DAS28, SDAI, CDAI, and Boolean) at Week 24 will be summarized by treatment group.

- The changes from baseline (absolute change) in the physical and mental component scores of the SF-36 at Week 12 and at Week 24 will be summarized by treatment group.
- The change from baseline (absolute change) in SF-36 scales at Week 12 and at Week 24 will be summarized by treatment group.
- The change from baseline (absolute change) in FACIT-Fatigue at Week 12 and at Week 24 will be summarized by treatment group.

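### At the predose Week 2 visit the two 150 mg arms have had the same treatment, so a supplementary pooled 150 mg column (planned n=132) would estimate the first-dose effect more precisely than the five-arm summary alone

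*Combined protocol and SAP*

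**What the plan says.** Section 3.1.1 (Study Overview) explains that ACR responses and disease activity scores are recorded at visits before the expected plateau, and gives the reason: "This will allow evaluation of potential differences in early clinical efficacy between the doses".

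The arms are defined in section 3.1.1 (Study Treatment Allocation) and section 3.1.2 (Blinding):

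- Group 3: "ALX-0061 150 mg s.c. injections (1 syringe [1.0 mL]) at Week 0 and q4w thereafter". At the alternate visits this arm gets "syringe A with placebo at Weeks 2, 6, 10, 14, 18, and 22".
- Group 4: "ALX-0061 150 mg s.c. injections (1 syringe [1.0 mL]) at Week 0 and q2w thereafter". Syringe A is filled "with ALX-0061 at Weeks 0, 2, 4, 6, 8, 10, 12, 14, 16, 18, 20, and 22".
- In both arms Syringe B (0.5 mL) is placebo at every visit.

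Footnote A of the Schedule of Assessments fixes the order within a visit: "All assessments are to be completed prior to study drug administration, except for subjects who discontinue study drug injections". Section 3.4.8 repeats that dosing comes last, and footnote M makes PK, biomarker and immunogenicity samples predose.

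The Schedule places joint counts, pain VAS, HAQ-DI, global assessments, routine laboratory tests (with CRP and ESR), PK and sIL-6R at Week 2, so the ACR and disease activity scores can be derived there.

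Section 3.6.4 then states: "The proportion of subjects achieving an ACR response of 20, 50, and 70 over time will be summarized by treatment group". The other efficacy scores over time are also summarised by treatment group. Nothing in the protocol text pools the two 150 mg arms at Week 2 or notes that they are identical at that point.

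**The concern.** The stated question for the early visits concerns doses, while the layout is by regimen. At Week 2 the two do not match: five columns describe four treatments. The 150 mg first dose is estimated twice from 66 subjects each instead of once from 132. The table also shows two 150 mg rates that will almost always differ, although no regimen difference yet exists.

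At stake is some precision in the one visit that gives a clean single-dose comparison (placebo, 75, 150, 225 mg), and a table that could be misread. Validity is not at stake.

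**Working it through.** **Inputs.** 66 subjects per arm, 1:1:1:1:1 (sections 3.3.8 and 3.6.8); Week 0 and Week 2 syringe contents (section 3.1.2); predose assessment (Schedule of Assessments, footnote A; section 3.4.8). The documents give no Week 2 response rates, so a common Week 2 ACR20 rate *p* of 10-25% is assumed and shown as a range.

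**1. The plan's own figure.** Section 3.6.8 claims more than 90% power for the Week 12 Cochran-Armitage test with rates 25/30/45/55/55%. Simulation (200,000 trials, two-sided 0.05) gives 99.5% with scores 0-4 and 99.1% with 4-weekly mg scores 0/75/150/300/450. With 15% drop-out counted as non-response it gives 97.7% and 96.4%. The claim holds, and this point does not touch it.

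**2. When the 150 mg arms diverge.**

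| | 150 mg q4w | 150 mg q2w |
|---|---|---|
| Week 0, Syringe A (1.0 mL) | active | active |
| Week 0, Syringe B (0.5 mL) | placebo | placebo |
| Week 2 assessments | before injection | before injection |
| Week 2, Syringe A | placebo | active |
| Active doses before Week 4 assessments | 1 | 2 |

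The true difference is zero at Week 2 by design, and need not be zero from Week 4.

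**3. Precision.** With equal variances, the variance of a 150 mg versus other-arm contrast is proportional to

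- separate: 1/66 + 1/66 = 2/66
- pooled: 1/132 + 1/66 = 1.5/66

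The ratio is 1.5/2 = 0.75. The standard error ratio is √0.75 = 0.866, a 13% reduction; equivalently 1/0.866 = 1.155, so the unpooled error is about 15% larger.

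**4. In ACR20 points.** The 95% half-width of the difference is 1.96 × √[p(1−p) × 2/66] separately and 1.96 × √[p(1−p) × 1.5/66] pooled. The chance gaps are exact binomial probabilities for two arms of 66 with the same *p*.

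| Assumed *p* | Half-width, separate | Half-width, pooled | Chance gap ≥5 points between 150 mg arms | Chance gap ≥10 points |
|---|---|---|---|---|
| 10% | 10.2 | 8.9 | 31% | 6% |
| 15% | 12.2 | 10.6 | 39% | 11% |
| 25% | 14.8 | 12.8 | 48% | 19% |

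**5. Type I error.** A chi-square test between two identical arms of 66 rejects in about 5% of trials at every rate tried (4.6-5.1% for *p* from 5% to 45%). The separate columns inflate nothing.

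**The case against.** The case against is substantial.

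- *The planned summary is not wrong.* Summaries by randomised arm follow the ITT principle, are unbiased and have valid confidence intervals. This stands. A reader might infer bias or inflated type I error from the duplicated column; step 5 of the working shows neither.
- *Only one visit is affected.* Section 3.1.1 speaks of earlier time points in general. Joint counts fall at Weeks 2, 4, 6, 8 and 10 before Week 12, and the arms coincide only at the first. This stands: it would be wrong to say that the early dose comparison as a whole is split.
- *No Week 2 contrast of q4w with q2w is specifically planned.* Section 3.6.4.1 tests each dose against placebo for the primary endpoint, and section 3.6.4.2 gives secondary endpoints summary statistics. Remission over time is to be compared between groups, in a form left open, and all non-primary p-values are exploratory. This stands. A reader might infer that a Week 2 gap would mislead the choice of regimen. That is speculative, because section 2 bases the choice on safety and efficacy, the primary endpoint is at Week 12 and dosing runs to Week 22.
- *A reader can add the two columns, and exposure-response modelling (section 3.6.6) works from serum exposure.* Partly true. Adding counts recovers a pooled ACR rate. It is less simple for the median of a continuous score, and the modelling goes into a separate report that does not annotate these tables.
- *The SAP may already cover this.* Section 3.6.2 defers detail to it, and no separate SAP text is in the combined document. The absence of pooling is therefore established for the protocol text only.

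What survives is a precision gain for a purpose the protocol states. Pooling two randomised arms with the same treatment to date also preserves randomisation and ITT.

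**Conclusion.** The point holds as a small, nearly free improvement limited to the predose Week 2 visit. The five-arm summary there is valid but gives a 150 mg versus other-arm standard error about 15% larger than the design permits. Any difference shown between the two 150 mg arms at that visit is chance.

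That the arms are identical follows from the dosing and assessment schedules. The 13% reduction rests on 66 subjects per arm and equal variances. The figures in ACR20 points rest on assumed Week 2 rates of 10-25%.

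The documents do not support extending this to Week 4 or later, to the Week 12 trend test, or to the sample size. Nor do they show that the adverse event tables are deficient: section 3.6.7 plans treatment-emergent tables by arm, and a window ending at the second injection would be a new derivation.

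**What to change.** Keep all five-arm summaries. In section 3.6.4, and in the SAP before the Week 24 database lock, add for Week 2 efficacy and for the predose Week 2 laboratory, PK and sIL-6R summaries:

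- a supplementary pooled column, *150 mg first dose* (planned n=132), beside placebo, 75 mg and 225 mg;
- a footnote that the 150 mg q4w and q2w arms have had the same treatment up to that visit, so a difference between them is not a regimen effect.

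Week 4 onward, the primary analysis and the adverse event tables do not change. A pooled summary of adverse events with onset before the second injection is optional, since it needs its own onset window and tables.

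The cost is one extra column and a footnote in the Week 2 tables, with no new data, visits or subjects.

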### **Study Treatment Allocation**

At the Screening Visit, informed consent will be obtained from all subjects who are deemed potentially eligible for the study, according to the protocol-specified inclusion and exclusion criteria. At randomization, subjects will be reassessed and, if they meet all specified entry criteria, randomized to receive either ALX-0061 or placebo, as described below (also see section [3.3.8](#) for additional information on randomization).

Eligible subjects will be randomly assigned in a 1:1:1:1:1 ratio to 1 of the treatment groups listed below. As the highest dose of ALX-0061 will be administered via 2 injections q2w, subjects in Groups 1-4 will also be administered 2 injections q2w with 1 or both syringes containing placebo depending on the assigned treatment group to maintain the blind (see section [3.1.2](#)):

Group 1 (N=66)	Placebo Placebo s.c. injections (2 syringes [0.5 and 1.0 mL]) at Week 0 and q2w thereafter up to and including Week 22
Group 2 (N=66)	75 mg q4w ALX-0061 75 mg s.c. injections (1 syringe [0.5 mL]) at Week 0 and q4w thereafter up to and including Week 20. To maintain the blind, subjects in this group will also receive placebo s.c. up to and including Week 22 (1 placebo syringe [1.0 mL] at Week 0 and q4w thereafter in combination with the ALX-0061 injection; 2 placebo syringes [0.5 and 1.0 mL] at Week 2 and q4w thereafter).
Group 3 (N=66)	150 mg q4w ALX-0061 150 mg s.c. injections (1 syringe [1.0 mL]) at Week 0 and q4w thereafter up to and including Week 20. To maintain the blind, subjects in this group will also receive placebo s.c. up to and including Week 22 (1 placebo syringe [0.5 mL] at Week 0 and q4w thereafter in combination with the ALX-0061 injection; 2 placebo syringes [0.5 and 1.0 mL] at Week 2 and q4w thereafter).

Group 4 (N=66)

150 mg q2w

ALX-0061 150 mg s.c. injections (1 syringe [1.0 mL]) at Week 0 and q2w thereafter up to and including Week 22. To maintain the blind, subjects in this group will also receive placebo s.c. q2w up to and including Week 22 (1 placebo syringe [0.5 mL]).

Group 5 (N=66)

225 mg q2w

ALX-0061 225 mg s.c. injections (2 syringes [0.5 and 1.0 mL]) at Week 0 and q2w thereafter up to and including Week 22. These subjects will not receive placebo injections.

*Efficacy Discontinuation Criteria at Week 12, 16, or 20*

Any subject with < 20% improvement from baseline in both SJC and TJC (66/68 counts) at any of the visits at week 12, 16 or 20 will discontinue from the trial, but remain blinded to study drug assignment. The visit at which subjects will meet the efficacy discontinuation criteria, is defined as the Early Termination Visit for these patients. Following this Early Termination Visit, any future care will then be provided (outside of the study) at the discretion of the treating physician as part of usual clinical practice.

The blind will be maintained until the last enrolled subject completes the final evaluations and the database is locked.

At all visits, study drug is to be administered under supervision while the subject is at the study site.

In countries where open-label extension (OLE) study ALX0061-C203 is approved, subjects who complete the 24-week assessment period of the current study will be invited to roll-over. Details on the open-label extension (OLE) study are described in Clinical Study Protocol ALX0061-C203.

Each subject will stay in the study for approximately 37 weeks (up to 3 weeks of screening and 34 weeks after randomization). The end of the study is defined as the time of the last visit of the last subject participating in the study.

### 3.1.2. BLINDING

On the day of the Week 0 study drug injection, the IWRS will assign each subject by means of the randomization list to a treatment group in a blinded way. See IWRS Manual for further details.

All subjects are to receive 2 injections (Syringe A and Syringe B) in succession at each dosing day. Since the 225 mg dose of ALX-0061 exceeds the volume that can be administered in a single injection, the placebo and ALX-0061 groups will have 2 different combinations of dosing to ensure the double-blinded design. See Study Drug Manual for further details.

Therefore, there will be a total of 5 dosing combinations in the study, with 4 possible dose levels. These dosing combinations are shown below:

Syringes A and B contain 1 mL and 0.5 mL, respectively.

#### Placebo

**Syringe A** with placebo at Weeks 0, 2, 4, 6, 8, 10, 12, 14, 16, 18, 20, and 22.

**Syringe B** with placebo at Weeks 0, 2, 4, 6, 8, 10, 12, 14, 16, 18, 20, and 22.

#### 75 mg q4w

**Syringe A** with placebo at Weeks 0, 2, 4, 6, 8, 10, 12, 14, 16, 18, 20, and 22.

**Syringe B** with ALX-0061 at Weeks 0, 4, 8, 12, 16, and 20, and syringe B with placebo at Weeks 2, 6, 10, 14, 18 and 22.

#### 150 mg q4w

**Syringe A** with ALX-0061 at Weeks 0, 4, 8, 12, 16, and 20, and syringe A with placebo at Weeks 2, 6, 10, 14, 18, and 22.

**Syringe B** with placebo at Weeks 0, 2, 4, 6, 8, 10, 12, 14, 16, 18, 20, and 22.

#### 150 mg q2w

**Syringe A** with ALX-0061 at Weeks 0, 2, 4, 6, 8, 10, 12, 14, 16, 18, 20, and 22.

**Syringe B** with placebo at Weeks 0, 2, 4, 6, 8, 10, 12, 14, 16, 18, 20, and 22.

#### 225 mg q2w

**Syringe A** with ALX-0061 at Weeks 0, 2, 4, 6, 8, 10, 12, 14, 16, 18, 20, and 22.

**Syringe B** with ALX-0061 at Weeks 0, 2, 4, 6, 8, 10, 12, 14, 16, 18, 20, and 22.

In order to protect the integrity of the data, treatment assignment will be kept blinded for investigative sites, site monitors, subjects, Sponsor, and CRO until the final database lock (including the Follow-up Visit 12 weeks after the last dosing).

---

Identification of Sponsor and CRO personnel who will have access to the unblinded data of the Week 24 database lock will be documented prior to unblinding. The number of Sponsor personnel having access to the data will be limited.

All clinical laboratory samples will be analyzed by a central laboratory, except for ESR that will be measured via the local laboratory, by an independent laboratory representative who is not directly involved in the study.

Given the pronounced effect of an anti-IL-6 compound on the acute phase reactants, the results of CRP, ESR and fibrinogen tests will not be communicated to the investigational sites and CRO/sponsor (unless in case of an alert for CRP or fibrinogen), with the exception of the CRP and fibrinogen results at screening, which are needed for assessing the subject's eligibility for randomization.

Except for ESR, CRP, and fibrinogen, laboratory values outside the normal range will be flagged and clinical relevance will be assessed by the Investigator. If clinical signs and symptoms are present for which the Investigator needs to know the values of ESR, CRP or fibrinogen for medical care, he can request this information.

